## 8.1.3. Missing Data

Missing data will not be imputed by any method. All subject data will be collected on standardized case report forms.

## 8.2 Data Analysis

#### 8.2.1. Baseline Subject Characteristics

Subject demographics, baseline characteristics and medical history will be summarized descriptively. Mean and standard deviation will generally be reported for continuous variables; median and range may be reported instead if the data distribution is skewed. Frequencies and proportions will be reported for categorical variables.

#### 8.2.2. Safety

#### 8.2.2.1. Primary Safety Analysis

The primary safety analyses will be based on the 30-day incidence rate of Amputation-Free Survival for the safety study sample per 8.1.1. Survival rates, 95% confidence intervals, and Kaplan-Meier analyses will be reported.

## 8.2.2.2. Secondary Safety Endpoints Analyses

The secondary safety endpoint will be similarly summarized as described in 8.2.2.1.

Additionally, all serious and non-serious adverse events that are potentially device- and/or procedure-related, and/or related to the index limb will be summarized by type of event, severity, relationship to the device and/or procedure, and timing of event relative to the procedure date.

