Assessment of amputation and/or major re- intervention of the Stent Graft			V		V	$\checkmark$	V	V
Duplex Ultrasound Exam to assess Stent Graft patency 			V	1	√9	1		
All-cause mortality			V		1	٦	V	$\checkmark$

 Dual antiplatelet therapy is required for 3 months post-procedure. At a minimum, all subjects must be started on

DAPT at least 1 week before procedure or adequately pre-loaded with DAPT as per institution practice.  Prior to any re-intervention of the stent graft, an angiogram/image and wound photograph should be obtained for adjudication purposes.

TcPO2 will be measured at 2 constant points on the dorsum of the midfoot through the 12 month follow-up.

 Per ACC/AHA 2006 Peripheral Arterial Disease Guidelines

 Review of any hospitalizations or procedures involving the index limb, and/or potentially related to the device or procedure; all SAEs through 6 months. For patients out of area or who refuse to come in for this visit, a telephone

assessment should be conducted to capture as much information as possible at this time point.

 May be performed at any visit as standard of care, as indicated by clinical symptoms.

 Continuous wave doppler must be performed between 4 and 30 hours post-procedure to assess for acute thrombosis; any findings of acute thrombosis must be reported to the Sponsor within 24 hours of the exam. The sponsor must notify the FDA via email of any cases of acute stent graft thrombosis within 5 days of the event.  3 Month visit only

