# **11.0 Adverse Event Reporting**

## 11.1. General Definitions

An AE is defined as any undesirable clinical occurrence in a subject whether or not it is considered to be device related. In addition, the definition of AE applies to any event with an onset post study procedure or to any underlying diseases, present at baseline that exacerbate in severity post study procedure. Therefore, an underlying disease that was present at the time of enrollment is not reported as an AE, but any increase in the severity of the underlying disease is to be reported as an AE.

The following definitions for rating severity of adverse events will be used:

- Mild: Awareness of signs or symptoms, but easily tolerated; are of minor irritant type; causing no loss of time from normal activities; symptoms would not require medication or a medical evaluation; signs or symptoms are transient.
- Moderate: Interferes with the subject's usual activity and/or requires symptomatic treatment.
- Severe: Symptom(s) causing severe discomfort and significant impact of the subject's usual activity and requires treatment.

A serious adverse event (SAE) is defined as an event which leads to:

- Death due to any cause
- Life-threatening condition
- Results in persistent or significant disability/incapacity
- Requires in-patient hospitalization or prolonged hospitalization
- Necessitates an intervention to prevent a permanent impairment of a body function or permanent damage to a body structure
- Results in congenital abnormality

All SAE's will be reported.

**Device-Related Adverse Event**: an adverse event is considered to be device-related when, in the judgment of the investigator, the clinical event has a reasonable time sequence associated with use of the investigational device and is unlikely to be attributed to concurrent disease or other procedures or medications. It is reasonable to believe that the device directly caused or contributed to the adverse event.

**Procedure-Related Adverse Event**: an adverse event is considered to be procedure-related when, in the judgment of the investigator; it is reasonable to believe that the event is associated with the assigned study procedure and is not specific to the investigational device used. Other products, surgical techniques, or medications required specifically for the procedure are likely to have contributed to the occurrence of the event.

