**Concomitant Medication-Related Adverse Event:** an adverse event is considered to be concomitant medication related when, in the judgment of the investigator, it is reasonable to believe that the event is associated with concomitant medications used in conjunction with the investigational device and is not otherwise specific to the investigational device (e.g. bleeding associated with anticoagulation medication).

**Pre-Existing Condition-Related Adverse Event:** an adverse event is considered to be related to a preexisting condition when, in the judgment of the investigator, it is reasonable to believe that the event is associated with the subject's pre-existing condition and is not specific to the investigational device or procedure. Pre-existing conditions that are aggravated or become more severe during or after the procedure should be evaluated on a case-by-case basis to determine if the event may be more appropriately classified as device-related or procedure-related. **Unanticipated Adverse Device Effect (UADE):** Any serious adverse effect on health or safety or any life-threatening problem or death *caused by, or associated with the study device,* if that effect, problem or death was not previously identified in nature, severity, or degree of incidence in the Investigational Plan or any other unanticipated serious problem associated with a device that relates to the rights, safety, or welfare of subjects.

LimFlow, or its designee, in cooperation with the investigator, will assess all adverse events considered to be serious and device-related for potential reportability to the FDA and other regulatory authorities as an Unanticipated Adverse Device Effect (UADE).

The investigator should follow all unresolved serious adverse events until the events are resolved, the subject is lost to follow-up, the subject has withdrawn consent, or the adverse event is otherwise explained.

For purposes of this study, the following events are not considered adverse events, because they are normally expected to occur in conjunction with endovascular procedures / post-procedure, or are associated with customary, standard care of subjects undergoing these procedures:

- Early post-operative pain (within 24 hours post-index procedure) at the access site and/or related to position on procedure table
- Post-anesthesia/conscious sedation emesis, nausea, or headache (within 24 hours postindex procedure)
- Chest pain without associated ECG changes

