# **11.2.** Reporting of Serious and Non-Serious Adverse Events

## 11.2.1. General Reporting Requirements (Serious & Non-Serious Adverse Events)

All potentially device- and/or procedure-related adverse events (AE) and all serious adverse events (SAE) will be reported and monitored from the time of treatment through the 6 month follow-up visit. Any SAEs related to the index limb will be reported and monitored throughout the 2 year follow-up visit. The report should include: severity, duration, action taken, treatment outcome and

relationship of the adverse experience to the study device, procedure, concomitant medications, preexisting condition, etc. (i.e., unrelated, related or relationship unknown).

In the case of serious adverse events, procedure and/or device observations and malfunctions, medical record documentation (e.g. procedure notes, operative notes, discharge summary, relevant progress notes, imaging or lab studies) must be provided to sponsor or its designee.

The following criteria must also be adhered to by the investigator in the case of serious adverse events:

- The Adverse Event eCRF must be signed by the investigator.
- It is the responsibility of the investigator to inform their IRB of serious adverse events as required by their IRB procedures and in conformance with FDA and local regulatory requirements.

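### All serious adverse events are collected to 6 months, but the only planned adverse event summary leaves out those judged not related to the device, procedure or index limb

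*Combined protocol and SAP*

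**What the plan says.** **Collection.** Section 11.2.1 of the protocol requires that "all serious adverse events (SAE) will be reported and monitored from the time of treatment through the 6 month follow-up visit". Footnote 6 of Table 1 (section 6.3) agrees: "all SAEs through 6 months". Neither limits SAEs by cause in that period. After 6 months the scope narrows: "Any SAEs related to the index limb will be reported and monitored throughout the 2 year follow-up visit".

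**Attribution.** Section 11.2.1 asks for the relationship of each event to the device, the procedure, concomitant medication, a pre-existing condition and so on, graded as "unrelated, related or relationship unknown". Section 11.1 leaves the decision to the investigator. An event is device-related when "in the judgment of the investigator, the clinical event has a reasonable time sequence associated with use of the investigational device" and concurrent disease, other procedures or medications are unlikely explanations. Separate classes exist for events tied to concomitant medication and for those where "the event is associated with the subject's pre-existing condition and is not specific to the investigational device or procedure".

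**Analysis.** Section 8.2.2.2 states that "all serious and non-serious adverse events that are potentially device- and/or procedure-related, and/or related to the index limb will be summarized", by type, severity, relationship to device or procedure, and timing. Section 8 plans no other adverse event summary.

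**The concern.** The analysis rule is narrower than the collection rule, and the filter between them is a judgment made by investigators who know that every subject was treated with the device. The protocol calls the population frail (8.3), so a competing explanation will often be available for a serious event. Section 10.1 also says in advance that the LimFlow part of the procedure is not expected to add complications.

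Two examples show how the filter could work. Section 1.3.1 lists congestive cardiac failure as a possible device or procedure risk, but an investigator could assign an episode to pre-existing heart disease. Bleeding is the example that section 11.1 gives for its concomitant-medication class, while its procedure-related definition also mentions medications needed for the procedure. Whether a serious bleed away from the limb is summarized could therefore depend on which class is chosen.

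Safety is a stated objective (section 3.0). Under the plan as written, a reader of the results could not see how many SAEs were set aside, of what type, or on what attribution.

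**Working it through.** The plan gives no figure to reproduce, and no arithmetic applies. The check compares what is collected with what section 8 would put in an output.

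**Step 1: outputs planned in section 8.2.** Section 8.2.1 covers baseline characteristics. Section 8.2.2.1 covers amputation-free survival at 30 days. Section 8.2.2.2 covers amputation-free survival at 6 months and the filtered adverse event summary. Section 8.2.3.1 covers the effectiveness endpoints and conversions to other treatment. Only 8.2.2.2 tabulates adverse events.

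**Step 2: SAEs from treatment to 6 months, by kind.** An unknown relationship to device or procedure is read as potentially related.

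| Kind of SAE | Collected (11.2.1) | In the 8.2.2.2 adverse event summary | Elsewhere in section 8 |
|---|---|---|---|
| Related, or relationship unknown, to device or procedure | Yes | Yes | Not needed |
| Index limb, any cause | Yes | Yes | Not needed |
| Attributed only to concomitant medication, not index limb | Yes | No | No adverse event output |
| Attributed only to a pre-existing condition, not index limb | Yes | No | No adverse event output |
| Unrelated to any listed cause, not index limb | Yes | No | No adverse event output |

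The last three rows are the gap. The relationship axis of the 8.2.2.2 summary has only device and procedure, so the two other classes in section 11.1 have no place in it unless the event also involves the index limb.

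**Step 3: deaths.** A fatal SAE in the last three rows is outside the adverse event summary. If observed by 6 months, it counts in amputation-free survival (7.1, 7.2), unless the subject has already had a major amputation. In that case the composite has already failed and the death adds nothing. Table 1 collects all-cause mortality to 2 years, but the named survival endpoints stop at 6 months. The limb salvage endpoints at 9 and 12 months (7.3) do not include death.

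**Step 4: SAEs after 6 months.** Section 11.2.1 requires only index-limb SAEs, and the 8.2.2.2 filter admits those. The mismatch between SAE collection and SAE summary therefore lies between treatment and 6 months.

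**Step 5: other routes.** Section 11.1 says "All SAE's will be reported", but this stands among the event definitions and names no table, population or period. Sections 10.1.1 and 10.1.2 describe root-cause review of individual serious events; the second is limited to events related to procedure or device. Section 10.2 describes committee review of safety data. None of these is a tabulation.

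**The case against.** The strongest reply is that the filter is a stated and defensible choice. This is a descriptive pilot of up to 35 subjects with no hypothesis test, and a summary focused on device, procedure and limb answers its main question. The word potentially in 8.2.2.2 is wider than the device-related definition in 11.1, and 11.1 also asks for aggravated pre-existing conditions to be considered individually for reclassification. The Independent Safety Committee's list of data to review is open-ended. The sponsor must write progress and final reports (15.1.1). Nothing forbids an all-SAE table, and the data will exist if one is wanted later.

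Most of this stands, and it limits the size of the point. It does not remove it: every one of these routes leaves the all-SAE display to discretion.

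Three stronger readings are tempting, and the documents do not support them.

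- A reader might infer that events such as heart failure or sepsis will be lost. Many would stay in as potentially related, and sepsis arising from the index wound would enter through the index limb. Some could drop out; the plan does not say that they will.
- A reader might infer that SAEs judged unrelated go unseen. They are collected and reported to the sponsor, and the committee is not barred from reviewing them. What is missing is a planned summary.
- A reader might size the gap by crossing the three relationship answers with index limb yes or no, and conclude that just one of the six combinations drops out. Relationship is recorded against several causes, so an event marked as related to a medication or a pre-existing condition can also drop out. A count of classes also says nothing about the number of events.

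**Conclusion.** The point holds as a gap in descriptive safety reporting, of minor to moderate weight. SAEs judged not related to device or procedure and not involving the index limb are collected to 6 months but enter no planned adverse event summary, and investigator attribution decides which SAEs fall there. The number is unknown and cannot be estimated from the documents. No endpoint, population or sample size changes.

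It would be too strong to say that deaths are fully covered elsewhere. Amputation-free survival captures observed deaths through 6 months only where no major amputation has already counted, and deaths after 6 months are in no planned survival endpoint. It would also be too strong to call the safety endpoints biased, because neither uses relatedness.

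The conclusion assumes that section 8 is the whole analysis plan. The Safety Charter named in section 10.2 and the text of section 11.2.2 were not available. Either might add to case review, but neither is a usual place for planned tables.

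**What to change.** In 8.2.2.2, add a summary table and a subject listing of all SAEs from treatment through 6 months in the safety population of 8.1.1. Show event type, severity, timing and recorded relationship to each of device, procedure, concomitant medication and pre-existing condition. Keep the present related and index-limb summary as a subset.

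State the number of subjects under observation alongside the table. Some of the safety population will have less than 6 months of follow-up: section 6.4.1 follows subjects without an implant for 30 days or until related events settle, and section 6.6 allows exit on meeting a primary endpoint.

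The cost is one table and one listing from data already collected, with no new visits. The drawback is that they will contain background events of a frail population and have no comparator. They make attribution visible but cannot test whether it was right.

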## 8.2.3. Effectiveness

## 8.2.3.1. Secondary Effectiveness Analysis

The secondary effectiveness endpoints will be summarized for the effectiveness study sample per 8.1.2. Summary statistics for the Composite (rate and 95% confidence interval) will be reported. The proportion of LimFlow Stent Graft subjects who are converted to other treatment means due to technical failure will also be reported.

## 8.3 Sample Size Justification

It is generally recognized that a minimum of 10 completed subjects is sufficient to satisfy the goals of pilot studies such as the study described herein. Subjects will be carefully screened and followed to ensure all efforts are made to secure follow-up compliance in this frail subject population.

# 9.0 Data Management and Monitoring

# 9.1. Study Data Collection

Electronic Case Report Forms (eCRF) will be used to capture data for the safety and performance analysis. Sites will be required to maintain source documentation, in accordance with GCP guidelines and 21 CFR 812 to substantiate all data collected.

# 9.2. Site Data Monitoring and Quality Control

Primary data collection based on source-documented hospital chart reviews will be performed by the clinical research team, which may include sponsor or sponsor's designees. CRFs will be completed and forwarded to the sponsor within 14 days of the procedure or scheduled visit. The sponsor will provide adequate source document worksheets for capture of study-specific data during the procedure and follow-up visits that may not normally be collected during routine procedures.

The clinical site will be monitored periodically by the sponsor's personnel, or sponsor's designee, for protocol adherence, accuracy of CRFs, and compliance to applicable regulations. Any observations of non-compliance will be reviewed with the principal investigator. Any evident pattern of ongoing non-compliance may result in corrective actions by the sponsor, including potential study suspension, as deemed appropriate by the sponsor.

The sponsor will review significant new information, including unanticipated serious adverse events and ensure that such information is provided to the appropriate regulatory agencies, the investigators and to all reviewing IRBs as required by applicable regulations.

# **10.0 Safety Oversight**

# 10.1. Safety: Complication Analysis and Acceptance

Revascularization catheter procedures are known to have inherent risks of complications. No new or additional complications or adverse events are expected due to the LimFlow portion of the procedure.

## **10.1.1** Procedural Complications

If serious procedural complications or adverse events are observed, the events will be individually analyzed for root cause relative to the complete treatment procedure and then evaluated by the Independent Safety Committee and the Principal Investigator. The sponsor will assess these events for expedited reporting requirements.

## **10.1.2** Post-Procedural Complications

If serious complications or adverse events related to the procedure or device are observed during and through the 6 month follow-up, the events will be individually analyzed for root cause relative to the complete treatment procedure and then evaluated by the Independent Safety Committee and Principal Investigator. The sponsor will assess these events for expedited reporting requirements.

# 10.2. Independent Safety Committee (ISC)

An Independent Safety Committee will act as the medical monitor for this early Pilot Study. The ISC will consist of at least two (2) physicians with experience in surgical and/or endovascular treatment of CLI patients, who are independent from the Sponsor and are not investigators in the study. Whenever possible, the ISC will review data in a blinded fashion (i.e., blinded to site and subject ID, follow-up period, etc.) to minimize any potential bias. Specific roles, responsibilities and processes will be described in a Safety Charter, which will be agreed upon by ISC members and published prior to commencement of the study.

## Screening Responsibilities:

The ISC will review potential study candidates to evaluate their eligibility for the study, specifically to determine that no conventional distal bypass surgical or endovascular therapy for limb salvage is feasible due to the absence of a suitable distal target artery. Specific criteria to be evaluated by the ISC in this determination include, but may not be limited to:

- Baseline angiograms/images to evaluate the status and patency of the distal arterial bed (i.e., tibial and peritoneal arteries, dorsalis pedis artery, and plantar arteries)
- Wound photographs
- Medical history, including Rutherford Classification
- Clinical evidence of severe hemodynamic compromise in the index limb (e.g., TcPO2, pulse assessments)

#### **Endpoint Assessment/Adjudication:**

**Technical Success:** The ISC will review the procedural angiograms to assess stent graft/limb patency post-procedure to determine Technical Success.

**Outcomes Adjudication**: Reports of endpoint events will be reviewed and adjudicated, including but not limited to:

- Major amputation of the index limb
- Stent graft occlusion and/or acute stent thrombosis (via DUS and/or angiographic documentation)
- Death
- Major and minor re-interventions of the index limb
- Contrast-induced nephropathy
- Wound healing (progression, completion, confirmation).

## **Ongoing Safety Overview:**

The ISC will also review safety data while the study is in progress, including reports of any serious device- or procedure-related adverse events and/or any reports of device malfunction or failure. During the study, the ISC will be asked to ensure that the rights and welfare of the subjects are protected by providing recommendations concerning the continuation, modification, or termination of the study based on review of safety data.

